APPENDIX E: ABBREVIATIONS

Abbreviation	Terms
GCP	Good Clinical Practice
CRF	Case Report Form
SF-12	Short Form - 12
IRB	Institutional Review Board
EC	Ethics Committee
ERB	Ethics Review Board
BMI	Body Mass Index
IFU	Instructions for Use
AE	Adverse Event
SAE	Serious Adverse Event
UADE	Unanticipated Device Effect
ICH-GCP	International Conference on Harmonization – Good Clinical
	Practices
CV	Curriculum Vitae
HHS	Harris Hip Score
EQ5D	EuroQoL (Quality of Life)-5 Dimensions

This document provides the specific contents of the statistical analysis plan for a prospective, multi-center and non-inferiority clinical study on the safety and effectiveness of Trochanteric Fixation Nail Advanced (TFNA) manufactured by Johnson & Johnson Medical (Shanghai) Ltd. After all subjects are included and use the implant, the postoperative 24-week (\pm 4 weeks) follow-up is completed or the trial is terminated in advance and the database is forcibly locked, the statistical analysis report for preoperative preparation and postoperative 24-week (\pm 4 weeks) follow-up will be issued for registration application. Refer to the relevant tables, lists and graphs in the statistical analysis plan for the detailed specific analysis.

2. Clinical Study

2.1 Study objective

The primary objective of this study is to evaluate whether fracture union rate, evaluated 24 weeks after proximal femur fracture, for the investigational TFNA intramedullary nail is non-inferior to that for currently available control product PFNA-II in patients with proximal femur fractures.

2.2 Study design

The Trochanteric Fixation Nail Advanced (TFNA) is an implant designed to treat

proximal femur fractures and is currently in use in several regions worldwide (e.g., US, Europe). TFNA is manufactured using a titanium-molybdenum alloy (TiMo) that has not been used for a similar clinical application within China. The study is a prospective, multi-center, controlled, two-arm, randomized, non-inferiority study comparing the 24-week fracture union rate for proximal femur fractures treated with intramedullary nails using investigational devices (TFNA) compared to control devices (Proximal Femoral Nail Antirotation, PFNA-II), under a 10% non-inferiority margin.

2.3 Primary endpoint

The primary endpoint is the fracture union rate 24 weeks after surgery. Fracture union success is a composite endpoint; in order for an individual subject's surgery implanted with TFNA or PFNA-II to be considered successful he/she must satisfy all of the following criteria:

- 1. No focal tenderness or lengthwise percussion pain, or abnormal movement
- 2. The frontal/lateral X-ray examination shows the vague or no fracture gap, or the continuous callus passing across the fracture line
- 3. No deformation or breakage is found in the investigational product

2.4 Secondary endpoints

Secondary endpoints include the safety and effectiveness results, imaging outcomes and adverse events.

- Adverse events (type and frequency) for all adverse events will be compared for the study and control groups
- 24-week revision rate where revision is defined as removal of any component for any reason
- 24-week reoperation rate is defined as secondary surgery at the fracture site(s) for any reason
- Clinical Outcomes
- ► SF-12
- Harris Hip Score
- ► EQ-5D
- Radiographs: incidence of complications such as loosening or cut-out that require reoperation or revision.

3. Investigational Device

3.1 Investigational device

TFNA as the investigational product for this study, including:

- Short nails available in various diameters (Ø9, Ø10, Ø 11, Ø12 mm), lengths (170, 200, or 235 mm) and CCD angle (125°, 130° and 135°). The 235 mm short nail is available for left and right sides.
- Long nails available in various diameters (Ø9, Ø10, Ø 11, Ø12, Ø14mm), lengths (260-480mm in 20mm increments) and CCD angle (125°, 130° and 135°). All long nails are available for left and right sides.
- Head elements are available in blade and screw (both are 70-130 mm in length, available in 5mm increments)
- Locking screws (4.2mm diameter and available in lengths from 26-80mm (2mm increments) or 80-100mm (5mm increments)
- End caps available in 0, 5, 10 and 15mm lengths

3.2 Control device

PFNA-II as control product for this study, including:

- Short nails available in various diameters (Ø9, Ø10, Ø 11, Ø12 mm), lengths (170, 200, or 240 mm) and CCD angle (125° and 130°). The 240 mm short nail is available for left and right sides.
- Long nails available in various diameters (Ø9 and Ø10mm), lengths (260-340mm in 20mm increments and 340-420mm in 40mm increments) and CCD angle (125° and 130°). All long nails are available for left and right sides.
- Head elements are available in blade (70-120 mm in length, available in 5mm increments)
- Locking screws (4mm diameter and available in lengths from 16-60mm (2mm increments), 60-80mm (4mm increments) or 80-100mm (5mm increments)
- End caps available in 0, 5, 10 and 15mm lengths

4. Intended Use and Indications of the Product

The intended use for TFNA is the following:

Intended Use: intended for the treatment of proximal femur and combinations of proximal and shaft fractures of the femur

The indications of the TFNA are:

- Short Nails (lengths 170 mm, 200 mm, 235 mm)
- Pertrochanteric fractures (31-A1 and 31-A2)
- Intertrochanteric fractures (31-A3)
- 235 mm nails are additionally indicated for high subtrochanteric fractures

10/129

- Long Nails (lengths 260 mm 480 mm)
- Pertrochanteric fractures (31-A1 and 31-A2)
- Intertrochanteric fractures (31-A3)
- Fractures of the trochanteric area (31-A1/A2/A3) with diaphyseal extension
- Combined fractures of the trochanteric area (31-A1/A2/A3) and the femoral shaft (32-A/B/C)
- Pathological fractures, including prophylactic use
- Malunion
- Nonunion

5. Inclusion and Exclusion Criteria of Subjects

5.1 Inclusion criteria

Subjects who meet all of the following inclusion criteria will be eligible for participation in the study:

- 1) Age ≥ 18 years
- 2) Patients with unilateral proximal femur fractures that will be treated with intramedullary nail internal fixation
- 3) According to AO fracture classification, subjects with following fracture type:
- a. Pertrochanteric (31-A1 and 31-A2)
- b. Intertrochanteric (31-A3)
- c. Trochanteric area (31-A1/A2/A3) with diaphyseal extension
- 4) Subject must be comfortable with speaking and understanding questions and responses in an available translated language for patient reported outcomes (PROs)

5.2 Exclusion criteria

Subjects who meet any of the following criteria will be excluded from the study:

- 1) Subject does not provide voluntary consent to participate in the study.
- 2) The subject is a woman who is pregnant or lactating
- 3) Fractures where the operative treatment will occur more than three weeks after the primary injury
- 4) Patients with femoral head fractures and femoral neck fractures (AO classification 31-B and 31-C)

- 5) Pathological fracture (e.g., primary or metastatic tumor)
- 6) Serious soft tissue injury, judged by the investigator, will impact the union of the fracture, combined vascular injury, and combined osteofascial compartment syndrome.
- 7) Multiple systemic injuries judged by researchers not suitable for enrollment, or orthopaedic fractures in other bones at three or more sites
- 8) Revision surgeries (for example, due to malunion, nonunion or infection)
- 9) Concurrent medical conditions judged by researchers not suitable for enrollment, such as: diabetes, metabolic bone disease, post-polio syndrome, poor bone quality, prior history of poor fracture healing, etc.
- 10) Patients with anaesthetic and surgical contraindications
- 11) Patents known to be allergic to implant components
- 12) Patients who are currently using chemotherapeutics or accepting radiotherapy, use systematically corticosteroid hormone or growth factor, or long-term use sedative hypnotics (continuous use over 3 months) or non-steroidal anti-inflammatory drugs (continuous use over 3 months)
- 13) Intemperance judged by researchers not suitable for enrollment (e.g., excessive daily drinking or smoking, drug abuse);
- 14) Patients participated into other clinical trial in the previous 3 months;
- 15) Patients with bad compliance judged by researchers and cannot complete the trial according to the study plan, such as schizophrenia and dementia.

6. General Statistical Considerations

6.1 Study hypothesis

The primary endpoint analysis will be to demonstrate that the investigational device (TFNA) is non-inferior to the control device (PFNA-II) based on the fracture union rates at the 24 week follow-up visit. Non-inferiority test will be conducted based on a one-sided 97.5% confidence interval for the difference in the fracture union rate at 24 weeks between the study group and the control group.

The primary hypothesis is that, at 24 weeks after surgery, the investigational device (TFNA) is non-inferior to the control device (PFNA-II) based on the individual patient fracture union rate. Non-inferiority is defined by a test with a two sided 5% type I error and a 10% "margin of non-inferiority".

The study's null and alternative hypotheses are as follows:

$$\begin{split} H_o: \mathbf{P}_{\text{PFNA-II}} - \mathbf{P}_{\text{TFNA}} \geq 10\% \\ H_a: \mathbf{P}_{\text{PFNA-II}} - \mathbf{P}_{\text{TFNA}} < 10\% \end{split}$$

Where, $P_{PFNA-II}$ represents the fracture union rate among those receiving PFNA-II implant and P_{TFNA} denotes the fracture union rate among the recipients of TFNA.

Decision Criterion: The decision will be made to reject the null hypothesis H_0 and conclude the alternative hypothesis H_a if the one-sided 97.5% confidence interval for the difference in the fracture union rates between the control group and the study group is less than the margin of non-inferiority, 10%.

6.2 Sample size calculation

The sample size calculation is determined based on the primary endpoint using PROC POWER in SAS software version 9.3. It assumes that the fracture union rate at 24 weeks after surgery in the TFNA group would be equivalent to that of the PFNA-II group, and a common fracture union rate is approximately 95% or greater based on the literature review. With a non-inferiority margin of 0.10 and a power of 80%, this implies a sample size of 75 for the TFNA and of 75 for PFNA-II surgery groups, respectively. The sample size will be increased to 188 (94 per group) to accommodate potential 20% attrition.

The sample size applies to patients enrolled, randomized, and actually treated. Some patients who enroll in a study and are randomized may not be ultimately treated for various reasons. Patient enrollment and randomization will continue until the proposed sample size for treated patients is complete.

6.3 Analysis population

Full Analysis Set (FAS): The set of subjects determined following the intent-totreat (ITT) principle refers to the data set constituted by all subjects who participate in the randomized study and receive the investigational product (implant) (i.e., ITT population defined in the protocol).

Per Protocol Set (PPS): Refers to the subgroup of treatment population who completes the trial and excluded the population that seriously violates the protocol (which means that study subjects violating the inclusion criteria or meeting exclusion criteria, loss to follow-up during the trial, cross enrollment, out-of-specification use of investigational products, out-of-window time, etc.).

Safety Set (SS): Set of all subjects who participate in the study and use the investigational products and undergo at least one safety evaluation after baseline. (The definitions of SS and FAS are the same. Therefore, SS is not defined separately).

Actual Treatment Set (ATS): All patients who participate in the randomized grouping, complete the trial, actually receive the scheduled treatment in the study (not necessarily consistent with the results of randomized grouping) and do not seriously violates the protocol. On the basis of PPS, only cross-enrolled patients are included, but they are then grouped and analyzed according to their actual treatment, i.e., the actual treatment set is formed.

The primary efficacy analysis will be based on FAS, PPS and ATS (if applicable). All baseline demographic data and secondary efficacy indicator analysis will be performed on the basis of FAS, and the safety evaluation will be performed on the basis of FAS.

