10.8. Analysis Sets

All subjects who met the inclusion and exclusion criteria will be eligible for enrollment and will be randomized to either the investigational (TFNA) or the control (PFNA-II) group. The following two analysis sets have been defined for this study:

1) Intent-to-Treat (ITT) Population

This analysis set includes all subjects randomized and implanted with a protocol specified implant, TFNA or PFNA-II. It includes the patients who were treated and withdrew prior to

week 24 due to various reasons. If a patient is randomized to one treatment group, but receives the other group for any reasons, the patient is considered to be part of the treatment group as received. This analysis set will be the primary one for the secondary safety analysis.

2) Per Protocol Population

The Per Protocol Population will consist of the subset of the ITT Population who complete 24 weeks of follow-up with no major protocol deviations (including but not limited to: failure to satisfy all inclusion/exclusion criteria, failure to adhere to all protocol-required restrictions and prohibitions, receipt of prohibited concomitant procedures or therapies, and non-compliance to protocol-specific procedures) as determined by a review of subject data.

This PP population will be the analysis set for conducting the primary and secondary effectiveness endpoint analyses.

Separately from these two populations, any subjects who are enrolled into the study but who do not receive one of the study devices will be summarized separately. This summary will include demographics and reasons for not receiving a study device.
The figure below illustrates these populations:

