6.4 Detailed rules for determination of analysis population set and flow chart

- (1) No investigational device is implanted: Subjects obtain random numbers but do not use any study-related treatment (implantation study group, control group or third party products);
- (2) Violation of inclusion and exclusion criteria: The subjects do not meet the inclusion criteria or meet the exclusion criteria set in the study protocol, and the violation of this protocol will seriously affect the results of primary efficacy endpoints; the sponsor, investigators and statisticians will jointly determine through a blind review meeting whether the protocol violation will seriously affect the results of primary efficacy endpoints;
- (3) Loss to follow-up during the trial: Subjects are unable to obtain the fracture union rate 24 weeks after the primary endpoint surgery;
- (4) Cross enrollment: Subjects randomly assigned to the study group receive the control products, while subjects randomly assigned to the control group receive the investigational products;
- (5) Out-of-window time: The difference between the follow-up date at 24 weeks after primary endpoint surgery and the surgery date do not fall within the range of [140, 196], and the violation of this protocol may seriously affect the results of primary efficacy endpoints; the sponsor, investigators and statisticians will jointly determine through a blind review meeting whether the protocol violation will seriously affect the results of primary efficacy endpoints;
- (6) Out-of-specification use of investigational products: The specifications of the device implanted in the subject are not within the specification range specified in the study protocol;
- (7) Use of third party products: The subjects randomly assigned to the study group or the control group use third party products;

(8) FAS = Number of subjects enrolled in the trial - Number of subjects not implanted with any investigational device;

PPS = FAS - Number of subjects who seriously violate the study protocol;

ATS = PPS + Number of cross-enrolled subjects alone; ATS will be displayed if subjects are cross-enrolled in the trial, while ATS will not be displayed if no cross-enrollment occurs.

Number of subjects who seriously violate the study protocol = Violation of inclusion and exclusion criteria + Loss to follow-up during the trial + Cross enrollment + Out-of-window time + Out-of-specification use of investigational products + Use of third party products;

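### SAP 6.3 treats the FAS, the safety set and the protocol's ITT as one population; they differ, so the FAS safety tables can charge events to a device the subject did not receive

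*SAP*

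**What the plan says.** **Protocol 10.8 (Analysis Sets).** The ITT population is defined by what was implanted: "This analysis set includes all subjects randomized and implanted with a protocol specified implant, TFNA or PFNA-II". For a subject who gets the other arm's nail, "the patient is considered to be part of the treatment group as received". This is the main set for safety, and protocol 10.10.6 repeats that. Subjects who receive neither study device are summarized outside both analysis sets.

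**SAP 6.3 (Analysis population).** The FAS is "The set of subjects determined following the intent-totreat (ITT) principle", with the gloss "i.e., ITT population defined in the protocol". The SS is described as subjects who use the investigational products and "undergo at least one safety evaluation after baseline", but it is not built because "The definitions of SS and FAS are the same". Then "the safety evaluation will be performed on the basis of FAS". Only the actual treatment set (ATS) is said to be grouped by treatment actually given. It is formed from the PPS plus crossovers and is named only for the primary efficacy analysis.

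**SAP 6.4 (rules for the sets).** The one exclusion from the FAS is for subjects with nothing implanted, who "do not use any study-related treatment (implantation study group, control group or third party products". Crossovers and third-party-nail recipients are then subtracted from the FAS to give the PPS.

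**The concern.** In a device-registration trial the safety tables should show which device the events belong to. The SAP's AE percentages divide affected subjects by the total in the study or control group, so the grouping rule decides which device an event counts against. If the FAS holds subjects who received the other nail or a third-party nail, and they sit in their randomized arm, their AEs, device-related AEs, SAEs, UADEs, revisions and reoperations can be charged to a device they never had. The protocol's own safety set avoids this. The SAP says it uses that set, but its detailed rules build a different one.

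**Working it through.** **1. The plan's own figure.** Inputs from SAP 6.2 and 6.6: union rate 95% in both arms, margin 0.10, one-sided alpha 0.025, power 80%, attrition 20%.

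n = (1.960 + 0.842)² × 2 × 0.95 × 0.05 / 0.10² = 74.6, so 75 per arm. 75 / 0.80 = 93.75, so 94 per arm and 188 in total. Both figures reproduce, and the present point does not affect them. The 94 is used below as the arm size.

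**2. Who is in each set, and under which arm.**

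| Subject | Protocol ITT | SAP FAS (by 6.4) | SAP SS (wording in 6.3) | PPS | ATS |
|---|---|---|---|---|---|
| Crossover | In, by implant received | In; arm not stated, implied randomized | In, if evaluated after baseline | Out | In, by actual treatment, if no other serious violation |
| Third-party nail | Out, summarized separately | In; only the randomized arm is available | Out, on the wording about using the investigational products | Out | Out |
| Study nail, no post-baseline safety evaluation | In | In | Out | Out (no 24-week outcome) | Out |
| Nothing implanted | Out | Out | Out | Out | Out |

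The third-party entry under FAS follows from two places. Item (1) of SAP 6.4 names third-party products among the treatments that keep a subject out of the not-implanted group. Item (8) subtracts third-party users when going from FAS to PPS, which makes sense only if they were in the FAS.

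The crossover entry under FAS is an inference. It rests on the intent-to-treat wording, on Figure 1 and Table 1 running each arm from randomization to FAS to PPS, and on the ATS being singled out as grouped by actual treatment.

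So the FAS equals the protocol ITT only if there are no crossovers and no third-party nails. It equals the SS as worded only if, in addition, every implanted subject has a post-baseline safety evaluation.

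**3. Which tables are affected.** Tables 34–36 and 43 (AE, revision, reoperation, complications) are labelled FAS. Tables 79–94 (AE, device-related AE, SAE, UADE) carry no set label and fall under the general rule in 6.3. Tables 44–46 and 53 repeat AE, revision, reoperation and complications on the PPS, which drops these subjects. Device-related AEs, SAEs and UADEs have no PPS version.

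**4. Size, holding each denominator at 94.**
- Third-party recipient with an event: the event should be in neither arm. Shift = 1/94 = 1.06 points.
- Crossover with an event: it leaves one arm and joins the other. Shift = 2/94 = 2.1 points.
- Set size: with 1, 2 or 5 third-party nails among 188 implanted, the FAS has 188 subjects and the protocol ITT has 187, 186 or 183.

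**5. Illustration with assumed rates.** The documents give no crossover counts or AE rates. Assume true device-related AE rates of 10% (TFNA) and 5% (PFNA-II), and x crossovers each way. As randomized, the TFNA rate is [(94 − x) × 0.10 + x × 0.05] / 94, and the PFNA-II rate is the mirror image. For x = 5 this is 9.15/94 = 9.73% against 4.95/94 = 5.27%, a difference of 4.5 points instead of 5.0. For x = 2 it is 4.8, and for x = 9 it is 4.0. With assumed rates of 20% and 10%, the 10.0-point difference becomes 9.6, 8.9 and 8.1. Crossovers therefore pull a true safety difference toward zero.

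**The case against.** The strongest reply is that no SAP sentence says the FAS is analysed as randomized. Read literally, the gloss "i.e., ITT population defined in the protocol" brings in the protocol's rule, and crossovers are then counted under the nail they received. That stands to this extent: for crossovers the SAP contradicts itself rather than stating a wrong rule, and a programmer could build either version. A reader might infer that the SAP expressly charges crossovers to the assigned device; the text does not go that far. The gloss cannot cover third-party recipients, whom 6.4 keeps in the FAS although they received neither device. SAP 6.3 does speak of receiving the investigational product, which would exclude them, but 6.4 is the operational rule and says otherwise.

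A reader might also infer that every safety table runs on the FAS. That is not so: the PPS repeats give a comparison free of these subjects for four endpoints, and Tables 2 and 79 list protocol violators and AEs by subject. But removing subjects is not the same as attributing them, and the device-related AE, SAE and UADE tables have no such repeat.

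The third-party effect is further limited. Protocol 7.1.4 withdraws a subject who gets no study device, and SAP 7.4 codes revision and reoperation as missing without a 24-week visit unless an event was already recorded. Later events would therefore largely go uncounted. Early AEs would still be charged to the randomized arm. Finally, SAP 7.4 calls these analyses mainly descriptive, and no safety decision rule depends on them.

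**Conclusion.** The point holds. SAP 6.3 states two equalities, FAS with protocol ITT and SS with FAS, and both are false by the documents' own definitions. Placing third-party-nail recipients in the safety arms follows from SAP 6.4 and departs from protocol 10.8. As-randomized grouping of crossovers is implied, not stated. No planned summary safety table attributes either kind of subject by device received.

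The size is conditional: about 1.1 points per third-party event and 2.1 points per crossover event at 94 per arm, and zero if neither occurs. The plan provides for both with table rows and a dedicated set, but gives no counts; few are to be expected. This is worth correcting before analysis but does not threaten the trial.

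A reader might infer that the two documents also give opposite efficacy rules for crossovers. They do not. Protocol efficacy uses only the Per Protocol set, and protocol 7.1.4 makes crossover a major violation, so the protocol places crossovers in no efficacy arm. Its as-received rule belongs to the ITT, which it uses for safety. The SAP's PPS also drops crossovers, and its one explicit grouping rule, for the ATS, is by actual treatment.

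**What to change.** In SAP 6.3 and 6.4:

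- Define the SS separately as all subjects implanted with TFNA or PFNA-II, grouped by implant received, as in protocol 10.8. Use it for the AE, device-related AE, SAE, UADE, revision, reoperation and complication tables, and label each table with it.
- List third-party-nail recipients and their events separately, outside both device columns.
- State that the FAS is analysed as randomized for efficacy, and make 6.3 and 6.4 agree on whether third-party recipients belong to it.
- Delete both the sentence "The definitions of SS and FAS are the same" and the gloss "i.e., ITT population defined in the protocol". Removing only the first would still equate an as-randomized FAS with an as-received ITT.

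The cost is SAP wording, one population flag and one listing. The SAP already tabulates the devices used (Tables 21 and 22), so no new data are needed, and the sample size and the primary analysis do not change.
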